TF-CBT	80	80	80	80
Usual Care	80	80	80	80
Total by Country	320		320	
Total	640			

3C3. Study Conditions

3C3a. TF-CBT Condition. Children will receive the TF-CBT treatment protocol as tested in the TZ feasibility study and modified for KE (see 3C1c). [name], the KE-lay counselors, KE-based investigator ([name]), and the local trainers ([name], [name], & [name]) will oversee iterative modifications of the 12-week protocol that maintain fidelity and are culturally responsive and appropriate. A thorough overview of TF-CBT (Appendix D) and the TZ TF-CBT protocol (Appendix B) are included with this proposal and briefly described here. The intervention is delivered in 12 1.5-hour group sessions and 3 1-hour individual sessions, provided over 12 weeks. During weeks 1-8, guardian and child groups (8 participants in each) are run separately and concurrently with guardians and children earning the same skills. In the final 4 groups (groups 9-12) they participate in conjoint child-guardian activities. The trauma narrative, gradual exposure component is conducted in individual visits with the child (which are weekly and begin after group 4; see Appendix B), so that

the child can talk privately, one-on-one, with a counselor about the details, thoughts, and feelings related to their parent(s) death(s) and other traumatic events and so that other children are not triggered or traumatized by another child's narrative details. In groups 5-8, the children review, with counselor support, what they have done in the individual sessions (e.g., draw the picture again, write the story again), but no details are shared in the group. The group intervention is efficient (e.g., can provide treatment to 8 children-caregiver dyads with 3 counselors), culturally responsive (e.g., group delivery, modified analogies), and normalizing, as it includes other children/guardians with similar problems. The inclusion of the 3 individual sessions after trust is built, as with other group-based trauma treatment models⁹⁵ allows for individualization and privacy around specific trauma narrative details.

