3C4b. Assessment: Lay Counselors. In addition to clinical outcomes, we examine implementation factors that may affect clinical outcomes and, by measuring them in this RCT, we establish a benchmark for future implementation efforts. Implementation outcomes, as detailed below, include child and guardian attendance at groups (which may vary across countries; urban vs. rural settings), lay counselors' knowledge and fidelity to TF-CBT, and the lay counselor-supervisor relationship. Lay counselors will complete measures assessing knowledge and the supervisory relationship with the local trainers (see Table 4). These measures are administered to the lay counselors by the project coordinator (PC) in each site via paper and pencil self-report format and will be returned to the PC in a sealed envelope. Self-report fidelity data will involve lay counselors completing the group reports after each TF-CBT group session and emailing these reports to the local trainers and to [name] and [name], within two days of the group. Lay counselors audiorecord all sessions digitally. The electronic files are collected by the PC on a jump drive. Three child and 3 guardian sessions (6 total) will be randomly selected from each group by [name] (remotely) and will then be coded by the data entry person, who also serves as the independent coder and will be trained by Drs [name] and Cohen in TF-CBT coding procedures.

3C4c. Data Collection from Children and Guardians. As in our other research, interviewers who have experience in working with children and a college degree in a field related to data management or social services are selected. Interviewers will undergo one week of training. Interviewers receive training in issues of research confidentiality, protocols, ensuring common understanding of questions, and standard ethical procedures (see Human Subjects for more information and Appendix C for example training documents). Interviewers will not be allowed to begin interviewing until they have been certified by [name] and [name] on all procedures and passed practice interviews (see Appendix C: Interview Training Log).

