Implementation Outcomes	Objective Fidelity; RC	TF-CBT Checklist Scoring Sheet—TZ Group Version . The original TF-CBT Checklist Scoring Sheet, used in prior TF-CBT studies and has a well developed coding manual ¹¹⁴ . The intraclass correlations for the parent and child sessions were .80 and .79, respectively. Our team has revised this coding measure for coding group delivery of TF-CBT, based on the 12-week protocol used in the feasibility study. The coding measure has been piloted by the feasibility study lay counselors. Inter-rater reliability was acceptable. Our team is currently refining and testing this measure (to be completed 9/2011). As this measure is under revision, the original is included in the Appendix.	3 random selected sessions/group
	Self-report of Fidelity, Attendance; LC	TF-CBT Group Report—Child and Guardian Forms . These group report forms were developed for lay counselor self-report of fidelity to TF-CBT. It allows for self-report of (1) components covered for each group; (2) time spent on each topic; (3) notes on each component; (4) participant attendance; (5) short subjective report on response of each participant (child or guardian, depending on the form). Examples of 6 groups are included in Appendix A. †	Each TF-CBT group
	Acceptability; G	Exit Interview Guide . We plan to use the exit interview that was used in the feasibility study to assess acceptability and appropriateness. The exit interview solicits guardian feedback about the TF-CBT intervention. †	12w, TF-CBT only
	Counselor Knowledge, LC	TF-CBT Knowledge Test . In collaboration with [name], our team has developed a short TF-CBT knowledge test that asks about specific TF-CBT components in which lay counselors are trained and are provided in the TF-CBT group. This test was piloted by the feasibility study lay counselors (N=3), who performed at 95%, collectively, on the test.	Post-T [#] ; Post C1
	Supervisory Relationship, LC	Supervision Alliance Scale ¹¹⁵ (SAS). The SAS has 12 items; drawn from two scales ^{116 117} . The 12-item measure assesses the counselor-supervisor relationship and has demonstrated predictive value for burnout and turnover intention and has a Cronbach's α of .95 ¹¹⁵ .	Post C1; Post C2

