These aims would be tested by adding country and rural or urban setting as predictors at Level 2. These analyses would test whether country or setting explain between-condition differences in treatment outcomes at

a specific time point, and for the growth models, whether they explain differences between conditions in the rate of change over time.

Aim 3. Examine the impact of implementation factors (e.g., TF-CBT fidelity, lay counselor-supervisor relationship, child/guardian attendance) on outcomes.

Analyses for Aim 3 will focus on how implementation variables (such as attendance, fidelity, provider knowledge) are related to outcomes at 12-14 weeks (end of TF-CBT) and at the follow-ups. These analyses will be restricted to those in the TF-CBT condition. These Aims are tested by expanding the models described in Aims 1 and 2, above, to include implementation variables at both the individual level (such as attendance) and the group level (TF-CBT fidelity). For example, MLM equations that look at implementation effects on post-treatment levels of symptoms could be:

Level 1:	$Symptoms_{ig} = B_{0g} + B_{1g}PreSx + B_{2g}Cov + B_{3g}Attendance + e_{ig}$
Level 2:	$B_{0g} = \pi_{00} + \pi_{01}Fidelity + r_0$ $B_{1g} = \pi_{30}$ $B_{2g} = \pi_{30}$ $B_{3g} = \pi_{30} + r_2$

These models test how attendance during treatment and fidelity of the treatment provider influence symptoms at 12-weeks and at follow-ups, treating the intercept and the effects of attendance as random effects, and the

effects of pre-treatment symptoms and covariates as fixed effects.

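### The sessions coded for objective fidelity are drawn at random with no stated stratification by treatment block, so many child-stream draws miss a block and the score may carry avoidable noise

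*Combined protocol and SAP*

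**What the plan says.** The treatment has twelve group sessions and three individual ones (3C3a): "The intervention is delivered in 12 1.5-hour group sessions and 3 1-hour individual sessions, provided over 12 weeks". All are recorded (3C4b): "Lay counselors audiorecord all sessions digitally". For objective coding, 3C4b states "Three child and 3 guardian sessions (6 total) will be randomly selected from each group", drawn remotely. The Objective Fidelity row of Table 4 gives "3 random selected sessions/group". Neither place mentions strata.

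Section 3C3a shows that child sessions change in content. The individual trauma-narrative visits are described as ones "which are weekly and begin after group 4; see Appendix B". Then "In groups 5-8, the children review, with counselor support, what they have done in the individual sessions". Finally, "In the final 4 groups (groups 9-12) they participate in conjoint child-guardian activities". For guardians, the text separates only weeks 1-8 from groups 9-12.

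Two further facts matter. Lay counselors also report their own fidelity after every group session (3C4b, Table 4). And under Aim 3 in 3C5b the models are extended "to include implementation variables at both the individual level (such as attendance) and the group level (TF-CBT fidelity" being the group-level example.

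**The concern.** A three-session mean depends on which sessions were drawn as well as on how well the group was delivered. If fidelity is easier to achieve in some blocks than in others, two groups delivered equally well can receive different scores because one draw fell mainly in early skills sessions and the other in narrative review.

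Objective fidelity has three uses in the plan. It is an implementation outcome that Aim 2 compares by country and setting, a candidate group-level predictor in Aim 3, and part of the benchmark for later implementation work (3C4b). Noise in a predictor pulls its slope toward zero, and 3C5c already concedes that group-level predictors have little power except for large effects. A group with no coded child session from groups 5-8 also has no objective evidence of how its narrative review was delivered.

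**Working it through.** The plan gives no figure for block coverage or for the reliability of the fidelity score, so there is none to reproduce. The calculations below assume that three sessions per stream are drawn without replacement from the twelve group sessions.

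**Inputs.** Three sessions drawn per stream (3C4b); twelve group sessions (3C3a); child blocks of 4, 4 and 4 sessions and guardian blocks of 8 and 4 (inferred from 3C3a); 40 TF-CBT groups (20 per region in 3C2; 320/8 = 40). Section 3C5c speaks of 20 clusters, which is a separate matter.

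**Child stream**
- Possible draws: C(12,3) = 220.
- All three blocks covered: 4 × 4 × 4 = 64, or 29.1%.
- At least one block missed: 156/220 = 70.9%, or about 28 of 40 groups (40 × 0.709 = 28.4).
- A given block, such as groups 5-8, missed: C(8,3)/220 = 56/220 = 25.5%, or about 10 of 40 groups (40 × 0.255 = 10.2).

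**Guardian stream, 1-8 and 9-12**
- A block missed: [C(8,3) + C(4,3)]/220 = (56 + 4)/220 = 27.3%.

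**Whole group, three blocks applied to both streams**
- Independent draws, some block uncoded in both streams: 3 × (56/220)² − 3 × (4/220)² = 0.1944 − 0.0010 = 19.3%.
- Independent draws, a block uncoded in at least one stream: 1 − (64/220)² = 91.5%.
- Same session numbers used for both streams: 70.9%.

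**Attenuation of the Aim 3 slope.** The documents give no block means or variances, so these figures are illustrations. Assume block means of 90, 75 and 85 and a true between-group SD of 5 (variance 25).
- Variance among blocks: mean 83.33; squared deviations 44.4 + 69.4 + 2.8 = 116.7; divided by 3, 38.9.
- Variance that block mix adds to a mean of 3 from 12: (38.9/3) × (9/11) = 10.6 (SD 3.3).
- One stream: reliability 25/(25 + 10.6) = 0.70, attenuation about 30%.
- Both streams drawn independently and averaged: added variance 5.3; reliability 25/30.3 = 0.825, attenuation about 17.5%.
- Block spread halved: added variance 10.6/4 = 2.65 for one stream (25/27.65 = 0.90) or 1.33 for both (25/26.33 = 0.95), so attenuation is about 10% or 5%.
- Blocks that score alike: zero.

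These figures isolate block mix. Session-to-session variation within a block and coder error would come on top under either draw.

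**Gain from stratifying.** Let within-block session variance be 1 and the block means −d, 0 and +d.
- Simple draw: S²/3 × (1 − 3/12) = S²/4, with expected S² = 1 + 8d²/11. The variance is 0.25 + 0.182d², which gives 0.25, 0.30, 0.43 and 0.66 at d = 0, 0.5, 1 and 1.5.
- One session per block: (1/9) × 3 × (3/4) = 0.25 at every d.

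Stratifying is never worse under these assumptions, and it is better whenever the block means differ.

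**The case against.** A reader might infer that 71% of groups have a phase of treatment without fidelity data. The documents do not support that, for three reasons.
- Six sessions are coded per group, and only about 19% of groups would have a block uncoded in both streams if the draws are independent.
- Counselor self-report covers every group session, so only the objective measure is sampled.
- The blocks are read from 3C3a and are not defined as fidelity strata. The guardian text supports only two.

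All three stand as limits on the claim, but they do not remove it. In weeks 1-8 the child and guardian groups run separately under different counselors (3C3a, 3C3b), so a guardian recording cannot show how the child narrative review was delivered. Self-report comes from the people being assessed, and Table 4 lists objective coding as a separate measure.

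A second tempting reading is that the fidelity slope shrinks by 30%. That figure rests on assumed block means, uses one stream only, and presumes that the Level 2 fidelity term is the objective score; 3C5b does not say which measure is meant. The group version of the checklist is still being refined. If it scores each session against the content due in that session, block differences may be small.

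It is also fair to say that a random draw is unbiased for the group's mean fidelity and is a legitimate design. What it adds is noise, not bias, in the score. Finally, a simple random draw is the plain reading of the text but is not spelled out; if strata were intended, a sentence would settle it.

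**Conclusion.** The point holds as a free improvement to a secondary measure. No block strata are stated. Under a simple random draw, about 71% of child-stream draws leave a four-session block without objective coding, about 25% leave groups 5-8 uncoded, and about 27% of guardian draws miss one of their two blocks. These coverage figures are firm, given the twelve-session frame and the blocks inferred from 3C3a.

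The effect on the analysis is much less certain. It runs from no attenuation, if blocks score alike, to about 30% for one stream under the widest spread assumed here; averaging both streams gives about 17.5% at that spread. In Aim 2 the effect is added noise in the fidelity comparisons.

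It would be wrong to infer that the treatment comparison is compromised: fidelity plays no part in the Aim 1 test.

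**What to change.** Keep six coded sessions per group and the remote random draw, but stratify it: one child and one guardian session from each of groups 1-4, 5-8 and 9-12. Use the equally weighted mean over blocks as the group's objective fidelity score wherever that measure enters Aims 2 and 3. State the same rule in 3C4b and in the Objective Fidelity row of Table 4, including how a recording of conjoint work in groups 9-12 counts toward the two streams.

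The cost is a short addition in each place. The recordings, the coder and the number of sessions coded do not change. The change does not add coding of the individual trauma-narrative visits; the rule should say whether those recordings are in the sampling frame.

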3C4a. Assessment: Children and Guardians. Clinical outcomes are assessed by child and guardian report at baseline, 12-14 weeks post-baseline (i.e., end of treatment for the TF-CBT condition, with a 2-week window), and at a 6- and 12-month follow up, to assess maintenance of any gains. Two trained interviewers at each site conduct all interviews. Interviewers will have minimal contact with lay counselors and will not attend the TF-CBT groups, so the intervention is not contaminated nor are the interviewers biased. The clinical assessment battery reflects what was used in the feasibility study (therefore many of the measures for this proposal have already been translated, back-translated, and approved by the Duke IRB and Kilimanjaro Christian Medical Center, for Moshi, TZ). One change that we believe enhances the assessment battery is inclusion of a locally derived tool to assess daily functioning activities, as other studies have demonstrated functional impairment resulting from CTG⁵³. The locally derived tool will be developed during the first year of the project, in both regions, following standardized qualitative measurement development procedures¹⁰⁵. An interview guide for development of the functioning tool was created during the feasibility study and is approved by the Duke IRB for use in Moshi, TZ (see Table 4 and Appendix A, for the interview guide and an example functioning tool from [name] & [name]'s other research).

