Our team has established procedures for monitoring interviewers during the RCT that decrease interviewer bias and drift (see Appendix C, Example Shadowing Log). The local PC in each site will shadow each interviewer for at least one child and one guardian interview each month. Interviewers will also be required to shadow a colleague’s interview once per month. Both interviewer and “shadower” independently complete the assessment forms to allow examination of adherence to the protocol. In each case, the “shadower” and interviewer debrief about the interview within 48 hours. Shadowing logs are maintained and reviewed monthly during the M-PI and PC calls.

The primary offices of interviewers and the data entry person and the lay counselors are physically separate so that they do not inadvertently discuss participants, the study condition, or an interview. This physical separation, along with training on the importance of maintaining confidentiality and clear communication of confidentiality to guardians and children, helps ensure non-biased study results. The Lead Investigators in both countries understand the importance of maintaining confidentiality and not contaminating either the intervention or research data by allowing interviewers and counselors to discuss, even casually, their work with participants. Investigators research teams will hold weekly calls with the interview team (via Skype) that are separate from the TF-CBT supervision calls with the local trainers.

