3C4d. Recruitment and Screening. All child/guardian participants will be identified by the two partner agencies in Moshi, TZ (TAWREF) and Bungoma, KE (ACE Africa). Children who are orphaned come to their attention through their existing support services (e.g., NGOs, church), from schools, or from other local groups. Staff from the partner agency make the initial contact with any potential participants and ask about willingness to receive information about the study. Children and guardians who are interested participate in a 2-level consent process conducted by the interviewers (see Human Subjects for additional information on recruitment, screening, and consent procedures). The two-level consent is similar to that used in our feasibility study, with added details on randomization, with the first level for screening (e.g., brief assessment of CTG and PTS). **Eligibility criteria** for study participation include: 1) child age between 7-13; 2) single or double orphan; 3) guardian adult (≥ 18 years old) who is willing to participate in either arm of the study and understands the randomization process ; 4) child’s parent(s) died *after* the age of 4 years (to ensure the child remembers the parent) and *before* the last 6 months (to avoid normal distress immediately post-death); and 5) a score of 10 or higher on the CTG measure or a score of 15 or higher on the PTS measure, by either child or guardian report. The inclusion criteria are designed to be broad, include even mild symptoms, but not to include children who do not need intervention. **Exclusion criteria** are few and include: 1) known developmental or cognitive disability, 2) the unwillingness of the child or guardian to be randomized, and 3) the unwillingness of the guardian to attend a 12-week group if randomized to the TF-CBT condition.

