If children are eligible and assent and consent are provided, remaining baseline assessment measures are administered (see Table 4) and participants are randomized. Randomization procedures occur prior to the screenings by the local PC and Drs. [name] and [name], reducing any randomization bias. Interviewers have a numbered stack of consent forms that are used in numerical order. Each consent form includes an attached envelope with randomization status (see Human Subjects for more information). Guardian-child dyads randomized to TF-CBT begin the 12-week group protocol within 2 weeks. All dyads are assessed again at 12-14 weeks post-baseline, 6-months, and 12-months post baseline. For all assessment meetings, children and guardians receive a small incentive for participation costing <\$2.50, (e.g., bag of sugar, laundry soap, pen).

Table 4. Study Measures (All Measures are included in Appendix A)

Domain; Respondent ^A	Measures & Indicators	Interval [*]	
Demo-graphics; G	Demographic Survey. We assess pertinent demographic information (e.g., guardian characteristics, years caring for child, home situation) using an established demographics measure from POFO, also used in the feasibility study. † +	BL, 12w, 6M, 12M	
Clinical Outcomes	Posttraumatic Stress; C, G	UCLA PTSD Index for DSM-IV¹⁰⁸ (UCLA PTSD-RI). The 38-item UCLA PTSD RI assesses trauma exposure and PTS symptoms. Response choices for PTS items are 0 - 4. The UCLA PTSD RI demonstrates good convergent validity and good to excellent test-retest reliability. Cronbach’s α in the range of .90. †	BL, 12w, 6M, 12M
	Behavioral Difficulties; G	Strengths & Difficulties Questionnaire¹⁰⁷ (SDQ). The SDQ is a brief behavioral screening survey (ages 3-16) with 25 items on 5 scales (Emotional Symptoms, Conduct Problems, Hyperactivity/Inattention, Peer Relationship Problems, & Prosocial Behavior). Response choices are from 0-2. The SDQ has been shown to have good discriminant validity and acceptable levels of test-retest reliability ¹⁰⁸ and a Cronbach’s α of .73 ¹⁰⁹ . †	BL, 12w, 6M, 12M
	Childhood Traumatic Grief, C	The UCLA Trauma Psychiatry Service Grief Inventory , (TPSG) is a 10-item measure that includes a subset of the items on the Expanded Grief Inventory ¹¹⁰ and is used to assess CTG symptoms. The scale has demonstrated moderate - high levels of internal validity, and has been used successfully with children aged 6 and older. †	BL, 12w, 6M, 12M

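### Interviewers enrol dyads on forms that carry the allocation envelope and also collect every outcome, so the conclusion in 3C4a that they are not biased does not follow from the safeguards given

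*Combined protocol and SAP*

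**What the plan says.** All references are to the combined protocol and SAP.

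- **Consent (3C4d).** Interested families "participate in a 2-level consent process conducted by the interviewers".
- **Allocation (3C4d).** "Interviewers have a numbered stack of consent forms that are used in numerical order. Each consent form includes an attached envelope with randomization status". The sequence is prepared in advance: "Randomization procedures occur prior to the screenings by the local PC" and two investigators. The remaining baseline measures are listed before randomization. The section refers to Human Subjects for more information.
- **Outcome assessment (3C4a).** "Two trained interviewers at each site conduct all interviews", at baseline, 12-14 weeks, 6 months and 12 months.
- **Reason given for unbiased assessment (3C4a).** The safeguard offered is this: "Interviewers will have minimal contact with lay counselors and will not attend the TF-CBT groups". The conclusion that the section draws from it is: "so the intervention is not contaminated nor are the interviewers biased".
- **Further safeguards (3C4c).** Interviewers are certified before they start. Their offices are separate from the counselors' "so that they do not inadvertently discuss participants, the study condition, or an interview". There is training on confidentiality and "clear communication of confidentiality to guardians and children". Interviewer calls are held apart from treatment supervision calls. The coordinator and the other interviewer shadow interviews monthly, a procedure said to reduce interviewer bias and drift.

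The supplied text does not say whether the envelope is sealed, who opens it, when it is opened, or which of a site's two interviewers follows up a given dyad.

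**The concern.** The plan itself treats the interviewer's role as a threat to validity. Section 3C1e says that the pilot's overlap of interviewer and counselor made its outcomes hard to attribute to the intervention, and 3C2 offers independent interviewers as a feature of the trial. Independence from counselors removes that overlap. It does not keep the interviewer from knowing the arm.

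The clinical outcomes in Table 4, including those in the 12-week comparison that 3C5c calls the primary hypothesis test, are child or guardian reports taken in these interviews. If an interviewer knew the arm, expectation could affect how questions are put or answers recorded. A resulting difference between arms would enter the treatment coefficient of the models in 3C5b, and nothing in those models could separate it from a treatment effect. Masking lost at enrolment cannot be restored at analysis.

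**Working it through.** No figure in the plan is at stake. The check sets each safeguard against the route in question, then counts the exposure and the cost of a change.

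**1. What each safeguard acts on**

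| Safeguard | Section | Acts on | Keeps the arm from the enrolling interviewer? |
|---|---|---|---|
| Sequence prepared before screening | 3C4d | Generation of the sequence | Not stated |
| Forms used in numerical order | 3C4d | Integrity of the sequence | No |
| Baseline measures listed before randomization | 3C4d | Baseline scores | Not after baseline |
| Allocation placed in an envelope | 3C4d | Concealment until opened | Depends on who opens it; not stated |
| Little counselor contact, no group attendance | 3C4a | Leakage from counselors | No |
| Separate offices, separate calls | 3C4c | Leakage from counselors | No |
| Confidentiality training and messages to families | 3C4c | Disclosure in conversation | No |
| Certification, shadowing | 3C4c | Conduct and recording, the latter in a sample of interviews | No |

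The 3C4d steps protect the sequence, and shadowing checks some of the recording. The reasons 3C4a gives for its conclusion concern counselors and groups only. None of the listed steps closes the path from envelope to enrolling interviewer to follow-up interview.

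**2. Exposure, before attrition**

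Inputs: 640 dyads (3C2b), three follow-up visits and two interviewers at each of two sites (3C4a).

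- Follow-up dyad assessments: 640 x 3 = 1,920, so 960 per site and 480 per interviewer.
- Done by the interviewer who enrolled the dyad:
  - interviewers keep their own dyads: 1,920
  - random split between the two: 1,920 / 2 = 960
  - crossed: 0

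These count exposure if the arm were learned at enrolment. They do not measure bias.

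**3. Load if follow-up is crossed**

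With an even split, each interviewer enrols 320 / 2 = 160 dyads and follows up the other's 160 x 3 = 480. The total is unchanged.

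**4. Load if the coordinator discloses the arm**

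- The intervention begins in year 2 (3C3b) of a 5-year plan. From the start of year 2 to the end of year 5 is 48 months. Less 12 months of follow-up, enrolment lasts at most about 36 months.
- Disclosures per site: 320 / 36 = 8.9 a month at the longest window, or 320 / 24 = 13.3 a month if enrolment takes 24 months (an assumption).

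**5. Colleague shadowing**

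Each interviewer shadows a colleague once a month: 2 per site x 24 to 36 months = 48 to 72 interviews. If every one were a baseline visit, the future follow-up interviewer would be present for 48 / 320 = 15% to 72 / 320 = 22.5% of a site's dyads. This is an upper bound.

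**6. Exit interviews**

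Table 4 gives the exit interview to the TF-CBT arm only, at 12 weeks. Table 2 has 80 + 80 = 160 TF-CBT dyads per site, so up to 160 exit interviews per site. The exit interview and the guardian's services questions (also Table 4) are possible further routes to the arm. Neither is established as one.

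**The case against.** The strongest reply is that the envelope details belong in Human Subjects, which 3C4d cites twice and which was not supplied. An envelope is a concealment device, the sequence is fixed in advance, and someone other than an interviewer may open it. This stands in part. A reader might infer that interviewers are unmasked, or that allocation is not concealed; the documents support neither, since they do not say that interviewers open the envelopes. What remains is that 3C4a draws its conclusion from separation from counselors, and that reason does not reach the envelope.

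A second reply is that the clause in 3C4a concerns only counselor contact and never claims masking. That is a fair reading of its context, but the clause is worded as a general conclusion about the interviewers.

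A third is that most scales described in Table 4 have fixed response options and that shadowing, with independent completion of the forms, is aimed at interviewer bias. Both limit the room for bias. Shadowing covers only a sample, however, and neither prevents knowledge of the arm.

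A reader might also want an inflated false-positive rate. That would need an assumed shift in scores, and the documents give no basis for one.

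**Conclusion.** The point holds in a limited form. The written procedure places the allocation with the people who assess outcomes, and no supplied safeguard keeps the enrolling interviewer from learning the arm and then assessing the same dyad three times. The no-bias conclusion in 3C4a therefore does not follow from the reasons given.

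The size of any bias is unknown. The exposure is between 0 and 1,920 follow-up assessments, depending on an assignment rule that is not stated and on whether the arm is learned at enrolment at all. The conclusion rests on the supplied text; Human Subjects could settle the envelope question. The point is worth fixing before enrolment because the main change adds no interviews. Confidence is medium.

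**What to change.** 1. **Cross the follow-up.** Assign each dyad's three follow-up interviews to the site interviewer who did not enrol it. The load stays at 160 enrolments and 480 follow-ups each with an even split.
2. **Move the envelopes.** Unless Human Subjects already provides an equivalent, have the site coordinator, who already takes part in randomization, hold the envelopes and disclose the arm after baseline, away from both interviewers.
3. **Order the visit.** Give the symptom and functioning scales before the services questions. Give the exit interview after 12-week scoring, by someone other than the dyad's follow-up interviewer. That person should not later shadow the dyad's visits. If it is the enrolling interviewer, apply the shadowing rule in both arms, since applying it to TF-CBT dyads alone would itself reveal the arm.
4. **Keep shadowing,** with an instruction not to discuss allocation in debriefs.
5. **Wording.** If neither these changes nor Human Subjects secures masking, replace the no-bias clause in 3C4a with a statement that interviewers are independent of counselors but that masking to arm is not assured. If Human Subjects does secure it, a cross-reference in 3C4a covers the envelope.

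**Cost.** About 9 to 13 coordinator disclosures a month per site (the upper figure assumes 24 months of enrolment), with coordinator capacity not given, and a second person for up to 160 exit interviews per site. The coordinator, who also shadows interviews, will know the arms. Some unmasking will remain through colleague shadowing (at most 15% to 22.5% of dyads per site at baseline, and only if step 2 fails) and through families who reveal their arm. Asking about services last protects only the visit at which it is done. Respondent bias is untouched, because dyads know their arm.
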